6.3 Description of analysis sets

Subjects will be included in the primary analysis set for the PK or PD variable in question if they complete the trial with no major protocol violations or deviations and they provide adequate data in support of the analyses described below.

Subjects will be included in the analysis of safety, if they have received at least one dose of study medication.

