3. STUDY PLAN AND PROCEDURES

3.1 Overall study design

This study will be conducted at a single center in the United States. It is a randomized, double-blind placebo-controlled study to assess the safety, tolerability, pharmacokinetics and pharmacodynamics of AZD6140 when given as single ascending oral doses to healthy Japanese and Caucasian male and female (non-childbearing potential) subjects. Approximately 40 subjects will be enrolled in order to obtain 20 subjects in each ethnic group. An attempt will be made to randomize an equal number of Japanese and Caucasian female subjects in each cohort.

Subjects in each ethnic group will be divided into 2 cohorts (Cohort A and B) of 10 subjects. Within each cohort, 8 subjects will receive single ascending doses of AZD6140 on 3 occasions. Two subjects in each cohort will receive placebo on 3 occasions. Consecutive single oral doses of either AZD6140 or placebo will be separated by a washout period of at least 5 days.

The study will consist of 5 visits (a screening visit, 3 dosing/PK visits and a follow-up visit). Subjects will receive a single oral dose of AZD6140 or placebo on Day 1 of Visits 2, 3 and 4. For Cohort A dosing is scheduled to progress from 50 mg at Visit 2 to 200 mg at Visit 3 to 400 mg at Visit 4. For Cohort B dosing is scheduled to progress from 100 mg at Visit 2 to 300 mg at Visit 3 to 600 mg at Visit 4 (see Figure 1). **Prior to the subject progressing to the next higher dose level, the safety results from the previous dose level will be evaluated by**

the principal investigator and study team physician of AstraZeneca. Refer to section 3.1.7 for specific stopping criteria.

At Visits 2, 3 and 4, subjects will remain at the Clinical Research Center (CRC) for 48 hours following dosing. There will be a washout period of at least 5 days between Visits 2 and 3 and between Visits 3 and 4. A follow-up visit (Visit 5) will be scheduled 7 to 14 days following the last dose of study drug.

In order to ensure that the **lowest** dose of study drug is the first dose administered, the subjects assigned to Cohort A will be randomized and dosed prior to the subjects assigned to Cohort B. Subjects assigned to Cohort B will be randomized and dosed **after** the results of the safety evaluations from Cohort A have been assessed and a decision to progress to the next dose level has been made.

The schedule of procedures and assessments are shown in Table 1.

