3.1.7 Stopping criteria for dose escalation

Prior to the subject progressing to the next dose level, the safety results from the previous dose level will be evaluated by the investigator and study team physician of AstraZeneca. Written approval from the sponsor will be obtained before dose escalation. Adverse events, with particular attention to events that may be caused by increases in bleeding times, clinical safety labs, and clinically significant changes in ECGs will be reviewed for each dose group. If the clinical safety laboratory measurements or adverse event rate with regard to possible effect on bleeding time is significantly disproportionate between the Caucasian group and the Japanese group to suggest that there may be an exaggerated difference in pharmacodynamic response to AZD6140 and if it is anticipated that subjects may experience significant risk from further dose escalations, then that dose group may be stopped from escalating after discussions with the investigator and the sponsor have taken place. If at least 50 % of any dose group have significant adverse events or laboratory abnormalities related to prolongation of bleeding effects (as judged by the investigator and AZ) escalation for that dose group may be stopped.

Figure 1 Study flow chart

[figure not shown]

Table 1 Study plan

Assessment	Screening Visit 1	Visits 2, 3 and 4						Follow-up Visit 5
	Max. 28 days prior to Day 1 of Visit 2	Day -2 (Visit 2 only)	Day -1	Day 1	Day 2	Day 3	Day 4	7 - 14 days after last dose
Informed Consent	X							
Demographics	X							
Inc/Excl. Criteria	X	X	X ^j					
Concomitant Medication	X	X	X	X	X	X	X	X
Medical/Surgical History	X							
Physical Exam	X	X						X
Brief Physical Exam			X ^j					
HIV, HBsAg, Hep. C Screen	X							
Drugs of abuse	X	X	X ^j					
12-lead ECG ^a	X		X	X	X	X	X	X
Vital Signs ^b	X	X	X	X	X	X	X	X
Pregnancy test (female subjects only) ^k	X	X	X ^j					X
Clinical laboratory assessments ^c	X	X	X ^j		X			X
Limited chemistry panel ^d				X				
Randomization ^e				X				
PK Sampling ^f				X	X	X	X	
ADP induced platelet aggregation ^g				X	X			
Bleeding Times ^h	X			X	X			
AZD6140/Placebo Administration				X				
Adverse event questioning		X	X	X	X	X	X	X
Genetic sampling ⁱ		X						

- a ECGs will be performed after 10 minutes in the supine position.
A single ECG will be performed at the following time points:
Visit 1 (Screening)
Visit 2: 48 and 72 hours post dose
Visits 3 and 4: Day –1 and at 48 and 72 hours post dose
Visit 5 (Follow-up)

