4.3.2 Bleeding time assessment

Bleeding time measurements using Simplate II[®] method will be determined at the times indicated in Table 4. Times will be recorded for each of the 2 incisions made by the device. If the pre-dose bleeding time is >9 minutes the subject should not be dosed and will be discontinued from the study.

If at the 24-hours post dose measurement the bleeding time is >60 minutes, a repeat assessment will be performed 48 hours post-dose. Additional repeat bleeding time assessments may be performed at the discretion of the investigator.

The methodology is detailed in Appendix C.

Table 4 **Schedule of bleeding time sampling**

Visit	Scheduled Time
1 (Screening)	Within 21 days prior to randomization
2	Pre-dose (within 60 minutes of dosing)
	4.5 hours post dose
	24 hours post dose
3	Pre-dose (within 60 minutes of dosing)
	4.5 hours post dose
	24 hours post dose
4	Pre-dose (within 60 minutes of dosing)
	4.5 hours post dose
	24 hours post dose

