6. STATISTICAL METHODS AND DETERMINATION OF SAMPLE SIZE

6.1 Statistical evaluation

Statistical analysis will be carried out by Biostatistics at AstraZeneca, Wilmington, Delaware using SAS (version 8). Summary graphics required for presentation in the text portion of the Clinical Study Report (CSR) will be done using Sigmaplot 2000. Other graphics intended for use as supplemental figures and individual profile figures will be done using SAS. A comprehensive Statistical Analysis Plan (SAP) will be prepared and finalized before unblinding and analysis of the data.

The goal of the PK analysis is to estimate the effect of ethnicity (Japanese vs. Caucasian) on exposure to AZD6140 and AR-C124910XX over the current dose range of AZD6140. Therefore, no formal hypothesis testing will be performed, though estimation of the ratio of exposure (Japanese/Caucasian) will be supported with two-sided 90% confidence intervals (CI). The analysis of pharmacokinetics will involve subjects included in the primary analysis

set. Estimation of the effect of ethnicity will be performed at each dose level in the study. Graphical methods will be widely used in support of estimation of effects and summary statistics where indicated below. Differences in gender will be addressed descriptively by comparing the PK parameters across gender within an ethnic group.

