6.4 Methods of statistical analyses

6.4.1 Pharmacokinetics

6.4.1.1 Primary analysis

The primary analysis of AZD6140 AUC will be based on log-transformed data using an ANOVA model with effects for dose, weight and ethnicity and subject within ethnicity as a random effect. The primary model will contain only the terms mentioned above. A model including a dose by ethnicity interaction term will also be explored and a term for gender may also be added depending on gender balance. The effect will be estimated using geometric means and two-sided 90% CIs for the ratio of AUC (Japanese/Caucasians) for each dose will

be estimated based on the primary model. The primary contrast will be between Japanese and Caucasians for each dose level. Because there are 2 dosing sequences (AZD6140 50 mg, 200 mg, 400 mg and AZD6140 100 mg, 300 mg, 600 mg) there will be two models of form similar to that described above one for each set of doses. Geometric mean AZD6140 plasma concentrations versus time by dose and ethnic group will be presented graphically. Individual plasma concentrations versus time by dose will be presented graphically. Adjustment for BMI may also be considered by including them as terms in the model. Individual profiles of AUC versus dose will be presented graphically. Dose normalized AUC versus dose and ethnic group will be presented graphically. Adjustment for BMI or weight may also be considered by including them as terms in the model. In the event that there are less than 6 subjects with estimated AUC, $AUC_{(0-t)}$ will replace AUC as one of the primary endpoints. $AUC_{(0-t)}$ and C_{max} will be analyzed in a manner similar to that mentioned above.

AZD6140 plasma concentrations, AUC, $AUC_{(0-t)}$, C_{max} , t_{max} , $t_{1/2}$, CL/F and Vz/F will also be summarized by dose using descriptive statistics detailed in the Statistical Analysis Plan.

Assumptions of normality of the log-transformed AUC, $AUC_{(0-t)}$, and C_{max} data will be explored in the primary analysis and, if necessary an appropriate non-parametric technique will be used to validate the results of the primary analysis.

AR-C124910XX AUC, $AUC_{(0-t)}$, t_{max} , $t_{1/2}$ and C_{max} will be analyzed in a manner similar to AZD6140.

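### Section 6.3 limits the PK and PD analysis set to subjects who complete the trial, so valid profiles from doses already taken are lost when a subject is discontinued at or after Visit 3

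*Protocol*

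**What the plan says.** Section 6.3 sets inclusion at the level of the subject: "Subjects will be included in the primary analysis set for the PK or PD variable in question". Two conditions are attached. The first reads "if they complete the trial with no major protocol violations or deviations"; the second asks for data adequate to the planned analyses. The wording distinguishes one variable from another. It does not distinguish one dose from another. Section 6.1 then ties the PK analysis to this same set: "The analysis of pharmacokinetics will involve subjects included in the primary analysis".

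Section 3.1 describes what a subject goes through: "The study will consist of 5 visits (a screening visit, 3 dosing/PK visits and a follow-up visit"). At each dosing visit there are 14 PK samples from pre-dose to 72 hours (Table 2) and five aggregometry samples including a pre-dose one (Table 3).

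Section 6.4.1.1 says "The primary contrast will be between Japanese and Caucasians for each dose level", and its model has "subject within ethnicity as a random effect".

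The protocol names several ways a subject can leave after an earlier full profile. Section 4.3.2: "If the pre-dose bleeding time is >9 minutes the subject should not be dosed and will be discontinued from the study". Section 3.3.5.1 lists safety reasons and refers to Section 3.1.7. Section 3.1.7 provides, for bleeding-related findings, that "escalation for that dose group may be stopped".

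No passage in Sections 6.3 or 6.4 lets a non-completer contribute data from a dose already received, and no passage defines completion of the trial.

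**The concern.** Each dosing visit is a self-contained single-dose experiment. A subject who gives a full profile at Visit 2 and is not dosed at Visit 3 has sound data for the first dose. Read as written, Section 6.3 removes that subject from the first-dose comparison because of something that happened later.

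Three things are at stake, in decreasing order of certainty:

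- Profiles already collected are discarded, and the interval at the earlier doses widens.
- The selection could be informative. If subjects with high exposure or strong response are the ones who stop, the completers in that ethnic group under-represent it, and the ratio at the earlier doses could be distorted.
- If completion means taking all three planned doses, a cohort whose escalation is stopped would have no completers. The synopsis allows the Caucasian subjects to escalate independently of the Japanese subjects, so this could happen in one ethnic group only. The ratio could then not be estimated at any dose of that cohort, including doses both groups had received.

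**Working it through.** **1. Is the restriction needed by the method?** The contrast is made dose by dose, and %PAI uses the pre-dose baseline (Section 6.2.3.1), sampled at each dosing visit. Both the primary model (Section 6.4.1.1) and the dose-proportionality model (Section 6.4.1.2) have a random subject effect. Such models accept subjects with one or two of the three doses, so the method does not force a completers rule.

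**2. Reproducing the planned precision.** Inputs from Section 6.5: two-sided 90% interval, 6 evaluable per ethnic group, AUC CV 21%, stated log-scale precision 0.2186, interval 0.80 to 1.24.

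Formula for a simple two-group comparison at one dose: half-width = t(0.95; 2n − 2) × SD × √(2/n).

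- With SD = √ln(1 + 0.21²) = 0.2077 and n = 6: 1.8125 × 0.2077 × 0.5774 = 0.2174, interval 0.80 to 1.24. This is within 1% of the stated figure.
- The SD that returns 0.2186 exactly is 0.2186 / (1.8125 × 0.5774) = 0.2089. It is used below so that the comparison starts from the protocol's own number.

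**3. Cost in precision at the first dose of a cohort (AUC).**

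| Subjects used | t | Half-width | 90% CI around a ratio of 1 |
|---|---|---|---|
| 8 v 8 (every profile kept) | 1.7613 | 1.7613 × 0.2089 × 0.5000 = 0.184 | 0.83 to 1.20 |
| 6 v 6 (two per group stop later) | 1.8125 | 1.8125 × 0.2089 × 0.5774 = 0.2186 | 0.80 to 1.24 |

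0.2186 / 0.184 = 1.19, so the interval is about 19% wider on the log scale. The planned mixed model also adjusts for weight and pools doses, so these figures are approximate.

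**4. How often might the bleeding-time rule alone remove someone?** The protocol gives no dropout rate, so this part is an illustration that rests on assumptions.

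- Appendix C gives a normal range of 2.3 to 9.5 minutes as mean ± 2 SD after log transformation. Log mean = (ln 2.3 + ln 9.5)/2 = 1.542; log SD = (ln 9.5 − ln 2.3)/4 = 0.355.
- Appendix C attributes about 40% of the variability to day-to-day differences and smaller parts to duplicates and to subjects. If each of those two is below 40%, the between-subject share lies between 20% and 40%. I assume these shares apply on the log scale.
- Simulated with readings rounded to 30 seconds, for subjects below 9 minutes at screening and at 9 or below before Visit 2, the chance of exceeding 9 minutes before dosing at Visit 3 or 4 is 4.8% at a 20% share and 4.0% at a 40% share.
- Over 32 active subjects (8 × 2 cohorts × 2 ethnic groups): 32 × 0.048 = 1.5 and 32 × 0.040 = 1.3.

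**5. Is that loss related to drug response?** Mostly not. Doses are at least 5 days (120 hours) apart and the mean half-life is 6 to 13 hours (Section 1.1). At 13 hours, 120/13 = 9.2 half-lives, and 0.5^9.2 leaves about 0.2% of the drug. A long pre-dose bleeding time at Visit 3 or 4 would mainly reflect baseline variation. Stops for adverse events or under Section 3.1.7 could be related to response, but the protocol gives no rate for them.

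**The case against.** **The design already allowed for the loss.** Section 6.5 randomizes 8 to active in order to have 6 evaluable, so 6 v 6 is exactly the precision promised. This stands: losing two subjects per group uses up the margin and does not break the planned precision. It answers the precision point only. It does not justify discarding data, and it does not address selection.

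**Dropouts can be replaced.** Sections 3.3.5.2 and 3.4.3 provide for replacement on the same treatment. This stands in part. Replacement is called for only when expected completers per ethnic group fall below 8, while 16 active subjects per ethnic group are planned, and is otherwise at the sponsor's discretion. It would not help a cohort whose escalation had been stopped.

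**A stopped cohort need not be empty.** A reader might infer that stopping escalation certainly leaves a cohort without PK or PD data. The protocol does not establish that. The reference from Section 3.3.5.1 to Section 3.1.7 lends support to treating such subjects as discontinued. It is equally possible to count as completers those who took every permitted dose and attended follow-up, and under that reading the problem does not arise.

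**The ratio is not shown to be pulled toward 1.** A reader might also infer this. The only loss rate that can be derived is chance variation in bleeding time after many half-lives of washout. Bias from response-related stopping is plausible but has no number behind it.

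**The primary objective is safe.** This stands. The safety set needs only one dose (Section 6.3), and bleeding time is analysed under Safety by dose and ethnic group (Section 6.4.3.2). A more sensitive ethnic group would still be visible there. The PK comparison is secondary, and Section 6.1 plans estimation without formal testing.

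**Conclusion.** The point holds for the secondary PK and %PAI comparisons, as something that should be fixed. As written, Section 6.3 discards valid earlier-dose profiles from any subject discontinued at or after Visit 3, and neither the design nor the model requires it.

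The demonstrated cost is precision: an AUC half-width of 0.2186 in place of 0.184 if two of eight per group stop after the first dose, which still meets the planned precision. Chance bleeding-time exclusions would account for about 1.3 to 1.5 of 32 active subjects under the Appendix C assumptions. Bias in the Japanese/Caucasian ratio is possible if stopping depends on exposure or response, and its size is unknown. Complete loss of a stopped cohort's PK and PD data follows only if completion means all three planned doses, and the protocol leaves that term open. The stronger conclusion, that the study would fail to detect a more sensitive ethnic group, is not supported, because the safety analyses do not use this set.

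**What to change.** Rewrite the first paragraph of Section 6.3 so that the PK and PD sets are defined by subject and dosing occasion. An occasion is included if the dose was received, the profile is adequate for the variable in question, and no major deviation affected that occasion, whether or not later doses are taken. Define completion of the trial, including the status of subjects whose escalation is stopped under Section 3.1.7, and keep the completers set as a sensitivity analysis.

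This should be settled before unblinding, so that the choice of set cannot appear to depend on the results. It needs no new data and changes no clinical procedure. The cost is one paragraph, unequal numbers per dose in the tables, and one additional sensitivity analysis.

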6.4 Methods of statistical analyses

6.4.1 Pharmacokinetics

6.4.1.1 Primary analysis

The primary analysis of AZD6140 AUC will be based on log-transformed data using an ANOVA model with effects for dose, weight and ethnicity and subject within ethnicity as a random effect. The primary model will contain only the terms mentioned above. A model including a dose by ethnicity interaction term will also be explored and a term for gender may also be added depending on gender balance. The effect will be estimated using geometric means and two-sided 90% CIs for the ratio of AUC (Japanese/Caucasians) for each dose will

be estimated based on the primary model. The primary contrast will be between Japanese and Caucasians for each dose level. Because there are 2 dosing sequences (AZD6140 50 mg, 200 mg, 400 mg and AZD6140 100 mg, 300 mg, 600 mg) there will be two models of form similar to that described above one for each set of doses. Geometric mean AZD6140 plasma concentrations versus time by dose and ethnic group will be presented graphically. Individual plasma concentrations versus time by dose will be presented graphically. Adjustment for BMI may also be considered by including them as terms in the model. Individual profiles of AUC versus dose will be presented graphically. Dose normalized AUC versus dose and ethnic group will be presented graphically. Adjustment for BMI or weight may also be considered by including them as terms in the model. In the event that there are less than 6 subjects with estimated AUC, $AUC_{(0-t)}$ will replace AUC as one of the primary endpoints. $AUC_{(0-t)}$ and C_{max} will be analyzed in a manner similar to that mentioned above.

AZD6140 plasma concentrations, AUC, $AUC_{(0-t)}$, C_{max} , t_{max} , $t_{1/2}$, CL/F and Vz/F will also be summarized by dose using descriptive statistics detailed in the Statistical Analysis Plan.

Assumptions of normality of the log-transformed AUC, $AUC_{(0-t)}$, and C_{max} data will be explored in the primary analysis and, if necessary an appropriate non-parametric technique will be used to validate the results of the primary analysis.

AR-C124910XX AUC, $AUC_{(0-t)}$, t_{max} , $t_{1/2}$ and C_{max} will be analyzed in a manner similar to AZD6140.

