6.5 Determination of sample size

Twenty Japanese subjects and 20 Caucasian subjects will be randomized into the trial. Ten subjects from each ethnic group will be assigned to each cohort. Eight subjects will be randomized to receive active AZD6140 (to achieve 6 evaluable) and 2 subjects will be randomized to receive placebo to AZD6140. The ratio of ethnic groups (Japanese/Caucasians) in terms of AUC and C_{\max} for the AZD6140 100 mg once daily doses can be estimated using a two-sided 90% confidence interval, assuming the following coefficients of variation (CV) (AUC: 21% C_{\max} : 20% [100 mg od based on trial 5130C5238]) with 6 subjects per ethnic group. Assuming these conditions hold, the log-scale precision for each of these intervals will be (0.2186 and 0.2092) and the 90% confidence interval around an observed ratio of 1 would be [AUC (0.80, 1.24) and C_{\max} (0.81, 1.23)].

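### The precision stated in section 6.5 is that of an unadjusted single-dose comparison, not of the primary PK model, and section 6.4.1.1 contradicts itself on whether weight is in that model

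*Protocol*

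**What the plan says.** **The model (Protocol 6.4.1.1).** Log-transformed AUC is analysed "using an ANOVA model with effects for dose, weight and ethnicity and subject within ethnicity as a random effect". The next sentence restricts the primary model to exactly those terms; a dose-by-ethnicity interaction is only to be explored. Because there are two dosing sequences, the model is fitted twice, once to 50/200/400 mg and once to 100/300/600 mg. The Japanese/Caucasian ratio and its two-sided 90% CI come from this model, and AUC(0-t) and Cmax are handled in the same way.

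**Weight again (Protocol 6.4.1.1, later in the section).** "Adjustment for BMI or weight may also be considered by including them as terms in the model".

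**The goal (Protocol 6.1).** "The goal of the PK analysis is to estimate the effect of ethnicity (Japanese vs. Caucasian) on exposure to AZD6140 and AR-C124910XX". Hypothesis testing is ruled out; the output is a ratio with a 90% CI.

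**The precision (Protocol 6.5).** With CVs of 21% (AUC) and 20% (Cmax) at 100 mg, "with 6 subjects per ethnic group": "Assuming these conditions hold, the log-scale precision for each of these intervals will be (0.2186 and 0.2092" on the log scale. Around an observed ratio of 1 the intervals are 0.80 to 1.24 and 0.81 to 1.23. Weight and the repeated doses are not mentioned.

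**The concern.** Three things do not fit together.

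1. The precision in 6.5 depends only on a CV, 6 subjects per group and the confidence level. The primary model has a between-subject covariate and three doses per subject. The interval the study report will print is therefore not the one the protocol plans for.

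2. Section 6.4.1.1 closes the primary model with weight inside it and then lists weight as something that might be added. Both cannot be true, and the choice would determine the headline PK estimate.

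3. Doses are fixed in mg. If the groups differ in mean weight and exposure depends on weight, the weight-adjusted ratio compares Japanese and Caucasian subjects at equal weight. The unadjusted ratio compares them at the same tablet dose. The goal in 6.1 does not say which is meant, and the plan attaches a CI only to the model-based ratio.

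At stake is what a reader may conclude about exposure in Japanese subjects at a given dose, and how precise that reader believes the estimate to be.

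**Working it through.** **Inputs from the protocol.** CV 21% (AUC) and 20% (Cmax), 6 evaluable per ethnic group, two-sided 90% CI (6.5); weight in the model, three doses per cohort model, no interaction (6.4.1.1).

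**Inputs not in the protocol (assumed).** d, the difference in mean weight in within-group SDs: 0 to 2. rho, the within-group correlation of weight with log exposure: 0 to 0.5. The correlation between doses within a subject (ICC): 0.5 and 0.7. The only average weight given is 60 kg, used for the starting-dose calculation in 3.2. The eligibility limits on BMI and weight in 3.3.2 are the same for both groups.

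**Step 1: reproduce the printed figures.** Half-width = t(0.95; 10 df) × SD × √(2/6), with t = 1.8125.

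| SD taken as | AUC | Cmax |
|---|---|---|
| CV | 0.2197 | 0.2093 |
| √ln(1+CV²) | 0.2174 | 0.2072 |
| Printed in 6.5 | 0.2186 | 0.2092 |

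The printed values imply SDs of 0.2089 and 0.1999, which round to 21% and 20%. Neither a normal quantile (0.199 and 0.190 with SD = CV) nor 8 per group (0.185 for AUC with t on 14 df) fits. The printed figures are an unadjusted two-sample t interval at one dose, and as such the arithmetic is sound.

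**Step 2: add weight, still at one dose.** Half-width = t(0.95; 9 df) × SD × √(1−rho²) × √(2/6 + d²/10), with t = 1.8331 and SD = 0.2089 for AUC.

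| d | rho | AUC half-width | CI around 1 |
|---|---|---|---|
| 0 | 0 | 0.221 | 0.80 to 1.25 |
| 0 | 0.5 | 0.192 | 0.83 to 1.21 |
| 1 | 0 | 0.252 | 0.78 to 1.29 |
| 1 | 0.5 | 0.218 | 0.80 to 1.24 |
| 2 | 0 | 0.328 | 0.72 to 1.39 |
| 2 | 0.5 | 0.284 | 0.75 to 1.33 |

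Cmax follows the same pattern: 0.241 at d = 1, rho = 0, and 0.209 at d = 1, rho = 0.5.

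**Step 3: pool three doses, as the primary model does.** Without an interaction term the model gives one ratio common to the three doses. Averaging over doses multiplies the half-width by √(ICC + (1−ICC)/3), which is 0.816 at ICC 0.5 and 0.894 at ICC 0.7. Here rho is the correlation of weight with a subject's mean log exposure.

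| d | rho | AUC, ICC 0.5 | AUC, ICC 0.7 |
|---|---|---|---|
| 0 | 0 | 0.181 | 0.198 |
| 1 | 0 | 0.206 | 0.225 |
| 1 | 0.5 | 0.178 | 0.195 |
| 2 | 0 | 0.268 | 0.293 |

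For example, 0.2521 × 0.8165 = 0.206. These values treat d as the difference realised in the sample. If d = 1 is instead the population difference and weights are drawn at random, the mean half-widths at rho = 0 are 0.218 (ICC 0.5) and 0.239 (ICC 0.7). If weight explains 20% of the variance they are 0.195 and 0.214. Either way the results fall on both sides of 0.2186.

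**Step 4: the quantity estimated.** If AUC varies as weight to the power b, a weight-adjusted ratio of 1.00 corresponds to an unadjusted ratio of (Japanese weight / Caucasian weight)^b. With assumed mean weights of 60 and 70 kg, this is (60/70)^(−0.5) = 1.08 and (60/70)^(−1) = 1.17. With equal mean weights it is 1.00, and the two log ratios agree in expectation.

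**The case against.** The strongest reply is that 6.5 is a conditional planning statement for one dose, and planning without covariates is ordinary. Eight active subjects per group are randomized ("Eight subjects will be randomized to receive active AZD6140 (to achieve 6 evaluable"), so the realised interval may be narrower than printed. Nothing is tested, PK is a secondary objective, and no decision rule depends on the half-width. All of this stands. It limits how much the mismatch matters but does not make the printed interval that of the primary model.

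The contradiction can also be called mild: the sentence closing the model puts weight in, and the later one nearly repeats a BMI sentence before it and may be a drafting leftover. That is a fair reading, but the text does not say so.

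Raw differences would also be visible, since 6.2.2 summarizes the PK parameters by ethnic group for each dose and 6.4.1.1 plots concentrations and dose-normalized AUC. True, but none of these is described as a ratio with a CI.

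A reader might go further and infer that weight is tied to ethnicity in this trial, that adjustment must therefore widen the interval, and that weight should come out of the primary model. The protocol supports none of these. It gives no weights by ethnic group. Steps 2 and 3 show that precision can move either way. The goal in 6.1 is compatible with a total ratio or with a ratio at equal weight, and prespecifying weight to separate ethnicity from body size is defensible.

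**Conclusion.** Two points hold without any assumption. The precision in 6.5 belongs to an unadjusted 6 v 6 single-dose comparison and not to the weight-adjusted three-dose model of 6.4.1.1. And 6.4.1.1 makes weight both a fixed and an optional term.

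The size of the precision mismatch cannot be fixed from the protocol, because the weight difference, the weight-exposure correlation and the within-subject correlation are all missing. At a realised 1 SD weight difference, with ICC 0.5 to 0.7 and rho 0 to 0.5, the AUC half-width is about 0.18 to 0.23 against the printed 0.2186. Larger weight differences push it higher.

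The third point is conditional. Only if mean weights differ and exposure depends on weight does the adjusted ratio depart from the ratio at equal mg dose, by a factor of 1.08 to 1.17 in the illustration. In that case the plan provides no unadjusted ratio with a CI to set beside it. The point is worth correcting because it concerns the main PK comparison and is cheap to correct; it does not invalidate the design.

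**What to change.** 1. In 6.4.1.1, state once whether weight is in the primary model, and delete or reword the later sentence so that it agrees.
2. Report both the weight-adjusted and the unadjusted Japanese/Caucasian ratio with 90% CIs for each endpoint and dose. Say which is primary and what each estimates: exposure at equal weight, or exposure at the same mg dose.
3. In 6.5, label 0.2186 and 0.2092 (0.80 to 1.24 and 0.81 to 1.23) as an unadjusted single-dose approximation. Alternatively, restate the precision for the primary model with the assumed weight difference, weight-exposure correlation and within-subject correlation written out.

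The cost is wording in two sections and one extra model run per endpoint, with no added subjects or samples. The downside is that there will be two ratios to interpret, so the primary one must be named before unblinding.

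### The primary PK model has no dose-by-ethnicity term, so each cohort yields one common Japanese/Caucasian ratio instead of the dose-by-dose ratios that the plan names as its primary contrast

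*Protocol*

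**What the plan says.** All of the following is in the protocol.

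- Section 6.4.1.1 specifies, for log-transformed AUC, an "ANOVA model with effects for dose, weight and ethnicity and subject within ethnicity as a random effect", and closes the list: "The primary model will contain only the terms mentioned above".
- The interaction has a different status: "A model including a dose by ethnicity interaction term will also be explored".
- The same paragraph promises "two-sided 90% CIs for the ratio of AUC (Japanese/Caucasians) for each dose will" "be estimated based on the primary model", and states: "The primary contrast will be between Japanese and Caucasians for each dose level".
- Because each cohort has its own dose sequence, "there will be two models of form similar to that described above one for each set of doses". One model covers 50, 200 and 400 mg, the other 100, 300 and 600 mg.
- Section 6.1 repeats the per-dose aim: "Estimation of the effect of ethnicity will be performed at each dose level in the study". It also says that there will be no formal hypothesis test.
- Section 6.5 plans the precision of the ratio at a single dose, 100 mg, with 6 evaluable subjects per ethnic group.
- Cmax and AUC(0-t) are to be analysed in a similar way, and so are the metabolite's parameters.

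**The concern.** The declared target is a ratio at each dose, but the model fixed to deliver it lets ethnicity act only as one shift common to all doses. Three identical lines in a results table, each labelled with a different dose, would look like evidence that the ethnic ratio is stable across doses. That stability would have been imposed by the model and not observed.

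The protocol does not itself take a constant ratio for granted. Section 6.4.1.2 fits a power model separately in each ethnic group, so the dose exponent may differ between groups. If it does, the ratio must change with dose.

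The protocol positively fixes a model that cannot produce its stated contrast, so this is more than a detail left to the SAP. An SAP would have to depart from one sentence or the other, and the choice should be made before the data are seen.

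**Working it through.** **1. The plan's own precision figure.** Inputs from section 6.5: CV 21% for AUC and 20% for Cmax, n = 6 per group, two-sided 90% CI. For a two-group comparison at one dose:

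half-width = t(0.95, 2n − 2) × SD × √(2/n), with 10 degrees of freedom.

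- AUC: 0.2197 with SD = CV, or 0.2174 with SD = √ln(1 + CV²). The plan states 0.2186, so both agree within 0.6%. The second gives a CI of 0.80 to 1.24, as stated.
- Cmax: 0.2093 with SD = CV. The plan states 0.2092, and the CI is 0.81 to 1.23, as stated.

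The sample-size section therefore describes a single-dose ratio.

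**2. What the stated primary model estimates.** For subject i at dose d:

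log AUC = δ(d) + β × weight + ε × ethnicity + subject(i) + error.

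Japanese minus Caucasian at dose d and equal weight is [δ(d) + ε] − δ(d) = ε. The dose term drops out. The ratio exp(ε) and its CI are the same at all three doses of a cohort. Two cohort models give two ratios; the plan promises six. This is algebra and needs no assumption about the data.

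**3. Numerical illustration (the ratios and variances are assumptions, not protocol figures).** Two hundred simulated cohorts, 8 active subjects per group, between-subject SD 0.17 and within-subject SD 0.12 on the log scale, no weight term:

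| | low dose | middle dose | high dose |
|---|---|---|---|
| True ratio | 1.00 | 1.25 | 1.56 |
| Additive model | 1.26 | 1.26 | 1.26 |
| With dose-by-ethnicity | 1.01 | 1.26 | 1.57 |

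The additive model targets the geometric mean, (1.00 × 1.25 × 1.5625)^(1/3) = 1.25. That is 25% too high at the low dose (1.25/1.00) and 20% too low at the high dose (1.25/1.5625 = 0.80). A single further simulated data set with weight in both models gave 1.428 at all three doses from the additive model, and 1.08, 1.43 and 1.88 from the interaction model.

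**4. Width of the interval.** Let w be the within-subject share of the total log-scale variance. With complete data and ignoring the weight adjustment:

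- variance of the common log ratio = (2/n) × SD² × [(1 − w) + w/3]
- variance of a single-dose log ratio = (2/n) × SD²
- SE ratio = √[(1 − w) + w/3]

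The protocol does not give w. Over an assumed range:

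- w = 0.2: √0.867 = 0.93, SE 7% smaller
- w = 0.3: √0.800 = 0.89, SE 11% smaller
- w = 0.5: √0.667 = 0.82, SE 18% smaller

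With n = 6 and SD 0.21, using the same t quantile, the half-width falls from 0.2197 to 0.1965 at w = 0.3 (CI 0.82 to 1.22) and to 0.1794 at w = 0.5 (CI 0.84 to 1.20).

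**The case against.** The best defence is that little depends on this interval. Safety and tolerability are the primary objective, PK comparison is secondary, and without a formal test no decision rule or error rate is affected. The objectives in section 2.1 do not say that the comparison is per dose, and section 6.1 describes the goal as the ethnicity effect over the dose range, which suits a common ratio. Earlier studies, mainly in Caucasians, found approximately linear PK, so a near-constant ratio is a reasonable working model, although it is untested in Japanese subjects. All of this stands, and it limits the severity.

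A reader might infer that a ratio changing with dose would go unseen. The documents do not support that. PK parameters are summarised for each dose by ethnic group (section 6.2.2), dose-normalised AUC is plotted by dose and ethnic group, the interaction model is to be explored, and the power model is fitted in each group. What is lost is a primary ratio and CI that are specific to the dose.

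A reader might also infer that the CI is simply too narrow. That holds only if the ratio varies with dose. If it is constant, pooling three doses is legitimate, the narrower CI is valid at each of them, and section 6.5 is merely conservative.

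Two readings that might save the text fail. The two models are one per set of three doses, not one per dose. And the interaction model, which could supply the per-dose ratios, is not the model to which the text assigns them.

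**Conclusion.** The inconsistency is real. As written, the primary analysis gives two cohort-level ratios where six dose-level ratios are promised, whatever the data turn out to be. The same holds for Cmax, AUC(0-t) and the metabolite's exposure parameters where the same form of model is used.

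The numerical harm is conditional. The bias at individual doses depends on how far the true ratio moves with dose, and nothing in the protocol indicates that size. The 7% to 18% smaller SE rests on an assumed within-subject share of 20% to 50%, complete data and no allowance for the weight term. Both are illustrations only.

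The point should be fixed before unblinding. It does not make the PK comparison unusable, since other per-dose displays are planned and PK is a secondary, estimation-only objective.

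**What to change.** For each cohort, make the primary model

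log(AUC) = dose + weight + ethnicity + dose × ethnicity + random subject within ethnicity,

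and take the per-dose Japanese/Caucasian ratios and 90% CIs from its dose-level contrasts. Weight must stay in: dropping it would turn a weight-adjusted ratio into an unadjusted one. Report the additive model as a secondary analysis, labelled as the average ratio across the cohort's three doses. Do the same for Cmax, AUC(0-t) and the metabolite's exposure parameters. This agrees with the per-dose aim in section 6.1 and the single-dose precision in section 6.5.

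The other valid reconciliation is to keep the additive model and relabel the primary contrast as the common ratio within each cohort, with sections 6.1 and 6.5 reworded to match.

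The cost is wording in section 6.4.1.1 and the SAP, with no new data. Under the first option the per-dose CIs become slightly wider, close to the width already planned in section 6.5 if 6 subjects per group are evaluable.
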